2.2 Rationale for CYP2D6 Genetic Testing and DNA Storage

The metabolism of brexpiprazole was shown to be mainly mediated by CYP3A4 and CYP2D6 according to in vitro metabolism studies, and CYP2D6 is known to have multiple genotypes with different enzyme activities. It has been clarified that CYP2D6 genotypes affect the pharmacokinetics of brexpiprazole. Therefore, the examination of CYP2D6 genotypes will be performed in this trial to investigate the influence of CYP2D6 genotypes on the safety and efficacy of brexpiprazole,

Rationale of Sample Storage for Biomarker Exploration 2.3

2.4 Trial Objectives

The objective of the trial is to evaluate the superiority of brexpiprazole 1 or 2 mg over placebo after a 10-week treatment regimen for agitation associated with dementia of the Alzheimer's type in patients who require medication, to investigate the safety of brexpiprazole, and to identify the optimum dose.

3 Trial Design

3.1 Type/Design of Trial

This is a multicenter, randomized, double-blind, placebo-controlled, parallel-group comparison trial to evaluate the efficacy and safety of brexpiprazole in patients with agitation associated with dementia of the Alzheimer's type who require medication. The overview of the trial design is shown in Figure 3.1-1.

The trial consists of a screening period, a treatment period, and a follow-up period. The investigator or subinvestigator will explain the details of the trial to a prospective subject (if the investigator or subinvestigator judges that the subject is incapable of providing informed consent or if the subject is hospitalized for reasons related to medical protection, the subject's legally acceptable representative must provide written consent, and even when written consent is obtained from the legally acceptable representative, the subject should be given an explanation appropriate to his or her level of understanding and, if possible, should also provide written consent form (ICF) and obtain written consent for

participation in the trial from the patient (or their legally acceptable representatives) and caregivers. The subject's clinical course will be followed in the same environment (see Section 3.4.2 Inclusion Criteria, 4) such as hospitalization in the same medical facility, institutionalization in the same care facility, and continued care at home from at least 3 weeks before baseline evaluation up to the completion of the examinations scheduled at the completion or discontinuation of IMP administration. After obtaining consent from the patient (or their legally acceptable representatives) and caregiver, the investigator or subinvestigator will perform the specified observations, tests, and investigations to confirm the subject's eligibility before IMP allocation. Subjects who are judged to be eligible in the screening examination and baseline evaluation will be randomized to the brexpiprazole 1 mg, brexpiprazole 2 mg, or placebo group. The IMP allocation will be performed using a dynamic allocation method to minimize bias in background factors (medical care category, prior use of antipsychotics, CMAI total score in baseline assessment) among the treatment groups. Duration of IMP treatment is 10 weeks. The subject will receive brexpiprazole or placebo for 10 weeks according to Section 3.2 Trial Treatments, and undergo periodic observations, tests, and investigations to assess efficacy and safety. The subject will return to the trial site 28 days after the completion of IMP administration for follow-up observation. Discontinued subjects will also undergo follow-up observation.

For subjects who discontinued the trial during the treatment period, the examination at discontinuation will be performed.

The trial period of each subject is from the date of informed consent to the end date of follow-up observation. If subjects have transitioned to the extension trial and commenced IMP administration, follow-up observation will not be performed. In such a case, the trial period is until the end date of evaluation at Week 10 (Day 71).

Protocol 331-102-00088

Figure 3.1-1 Trial Design

Follow-up observation will not be performed for subjects who have transitioned to the extension trial and commenced IMP administration.

3.2 Trial Treatments

3.2.1 Dosing and Regimen

The IMP will be administered orally as one tablet once a day for 10 weeks. The doses of brexpiprazole for each group is shown in Table 3.2.1-1. Although the temporal relationship between IMP administration and meals will not be considered, subjects should take the IMP at the specified time in so far as possible. Dose reduction is not allowed during the trial, and if there are tolerability issues, administration of the IMP will be discontinued.

Table 3.2.1-1Doses	ble 3.2.1-1 Doses of IMPs				
Group	Day 1–7	Day 8–14	Day 15–70		
Brexpiprazole 2 mg	0.5 mg	1 mg	2 mg		
Brexpiprazole 1 mg	0.5 mg	1 mg	1 mg		
Placebo	0 mg	0 mg	0 mg		

The dose will be increased to 1 mg after evaluation at Week 1 (Day 8) and to 2 mg after evaluation at Week 2 (Day 15)

3.2.2 Rationale for Dosing and Regimen

Doses and regimen were determined on the basis of the results of the 2 overseas trials (Trial 331-12-283 and Trial 331-12-284), as no significant differences due to ethnicity have been observed in the PK of brexpiprazole.

In Trial 331-12-283, the brexpiprazole 2 mg group showed a statistically significant improvement in change from baseline in CMAI total score compared with the placebo group. In patients with aggression in the baseline evaluation in Trial 331-12-283, improvement in the 2 mg group was greater than that in the placebo group.

These findings suggested that 2 mg might be the optimal dose in Japanese patients. Therefore, 2 mg was selected to verify superiority over the placebo group.

On the other hand, although the 1 mg group in Trial 331-12-283 did not demonstrate improvement greater than that in the placebo group among either the overall population or patients with aggression, in Trial 331-12-284, which was conducted using flexible doses, the 0.5 to 2 mg group showed greater efficacy than the placebo group among patients with aggression, raising the possibility that doses lower than 2 mg might be effective. On the basis of these findings, a 1 mg group was included so that information on the dose-response relationships in Japanese patients could be obtained and superiority over the placebo group can be confirmed if the 1 mg group demonstrates efficacy similar to that in the 2 mg group.

In the 2 overseas trials, a dose titration method with a low starting dose and gradual dose increase was used in consideration of safety in elderly subjects, who were the target subjects of those trials. In the 2 overseas trials, a dose titration method in which dosing started from 0.25 mg and was increased to the maximum dose of 2 mg over 4 weeks was used, and no apparent safety problems were noted up to 2 mg. Since this trial will be conducted in patients with aggression who have a strong need for medication among patients with agitation, a dose titration method in which the dose will be started from 0.5 mg, increased to 1 mg at Week 1 (after evaluation at Week 1 [Day 8]) and to 2 mg at Week 2 (after evaluation at Week 2 [Day 15]) was selected to reach 2 mg (which may become the optimal dose) as quickly as possible. The starting dose of 0.5 mg is 1/2 of the starting dose (1 mg) of brexpiprazole in schizophrenia, and conforms to the precautions and principles for medication in elderly patients with dementia described in the Practice Guideline for Dementia 2017²⁶: "depending on the type of medication, starting treatment at lower doses such as 1/2 to 1/4 of the doses recommended for younger patients should be considered." Trial visits were set to 1 week after the start of trial treatment before a dose increase to 1 mg and 2 weeks after the start of trial treatment before a dose increase to 2 mg, and dose titration will be performed with confirmation of subject safety.

The dosing regimen is oral administration once daily based on the PK and the 2 overseas trials.

3.2.3 Rationale for Duration of Treatment

Duration of treatment was determined on the basis of the clinical position of brexpiprazole therapy and taking the results of the 2 overseas trials into consideration.

Brexpiprazole is positioned as symptomatic treatment for patients who require medication. The Practice Guideline for Dementia 2017¹⁷ states that atypical antipsychotics including brexpiprazole "should not be continued without a compelling reason even if their efficacy is recognized." Therefore, long-term administration as maintenance therapy after improvement of symptoms is not considered.

However, in a repeated-dose trial in Japanese patients with schizophrenia, steady-state was reached from Day 10 onward, and thus a certain period is necessary to confirm if efficacy is sufficient after increasing the dose to 2 mg.

In the 2 overseas trials, after the brexpiprazole dose had been increased to 2 mg (maximum dose), brexpiprazole was continued for 8 weeks (12 weeks in total, including the 4-week dose titration period) until sufficient efficacy was confirmed, and the efficacy of brexpiprazole 2 mg had been demonstrated. Therefore, as in the 2 overseas trials, it was decided that for this trial administration would be continued for 8 weeks after reaching the maximum dose of 2 mg. As described in Section 3.2.2 Rationale for Dosing and Regimen, as administration of brexpiprazole will reach the maximum dose of 2 mg at 2 weeks, a total of 10 weeks was set as the duration of treatment.

3.3 Trial Population

3.3.1 Number of Subjects and Trial Population

A total of 407 male and female patients (brexpiprazole 2 mg, 148 subjects; brexpiprazole 1 mg, 111 subjects; placebo 148 subjects) with agitation associated with dementia of the Alzheimer's type who require medication will be enrolled in the trial.

3.3.2 Subject Number Assignment

3.4 Eligibility Criteria

3.4.1 Informed Consent

Written informed consent will be obtained from all subjects (or their legally acceptable representatives) on their voluntary decision. If the investigator or subinvestigator judges that the subject is incapable of providing informed consent or is hospitalized for reasons related to medical protection, the subject does not have to provide informed consent, but the subject's legally acceptable representative must provide written consent. Even when written consent is obtained from the legally acceptable representative, the subject should be given an explanation appropriate to his or her level of understanding and, if possible, should also provide written consent. Consent will be documented on a written informed consent form (ICF) with the subject's signature. The ICF will be approved by the same institutional review board (IRB) that approves this protocol.

The ICF for subjects and their representatives will comply with the International Council for Harmonisation (ICH) Good Clinical Practice (GCP) Guideline²⁷ and regional regulatory requirements.

Investigators or subinvestigators may discuss the possibility for entry with a potential subject (or their legally acceptable representative) without first obtaining consent. However, informed consent must be obtained and documented before initiating any procedure that will be performed solely for the purpose of determining eligibility for this trial, including withdrawal from current medication(s).

Furthermore, to facilitate management of patient compliance with the treatment regimen and the collection of patient information during the trial via the cooperation of their caregivers, the investigator or subinvestigator will explain the details of the trial to the caregivers of potential subjects by using explanatory materials designed for caregivers and obtain their written informed consent to cooperate in the trial. Potential subjects (or their legally acceptable representatives) and caregivers are free to refuse participation in the trial or withdraw from the trial at any time, without justification, and there will be no consequences to the further care of said patients.

After the investigator or subinvestigator (or designee) has provided appropriate essential information to the subject (or their legally acceptable representative), has fully explained the information in plain language, has provided them with the opportunity to ask questions, and has made a record indicating that these procedures were followed, the IRB-approved written ICF will be signed and dated by the subject (or their legally acceptable representative), caregiver, and person obtaining the consent (investigator, subinvestigator, or designee). If a trial collaborator has provided supplemental
explanation, the IRB-approved written ICF will also be signed and dated by the trial collaborator. The subject (or their legally acceptable representative) and the subject's caregiver will receive a copy of the signed ICF; the original shall be kept on file by the investigator or subinvestigator.

Subjects (or their legally acceptable representatives) and their caregivers may be asked to sign additional ICFs if the protocol is amended to significantly add or change procedures.

The investigator or subinvestigator will enter information on subjects for whom informed consent has been obtained into an interactive web response system (IWRS).

For CYP2D6 genetic testing, DNA storage, and biomarker sample storage, a separate ICF will be used for explanation, and written informed consent will be obtained from subjects (or their legally acceptable representatives) on their voluntary decision in a similar manner. CYP2D6 genetic testing is mandatory, and if subjects (or their legally acceptable representatives) have not consented to CYP2D6 genetic testing, they cannot participate in the trial. On the other hand, DNA storage and biomarker sample storage are optional, and the refusal of subjects (or their legally acceptable representatives) to allow DNA storage and/or biomarker sample storage will not affect trial participation.

3.4.2 Inclusion Criteria

Subjects must meet the inclusion criteria described in Table 3.4.2-1.

Tab	le 3.4.2-1 Inclusion Criteria
1	Patients who have provided written informed consent (or whose legally acceptable representative has provided written informed consent). If the investigator or subinvestigator judges that the patient is incapable of providing informed consent or is hospitalized for reasons related to medical protection, the patient's legally acceptable representative must provide written consent.
2	 Patients who meet both of the following diagnostic criteria: Diagnosis of "Dementia due to Alzheimer's Disease" according to the Diagnostic and Statistical Manual of Mental Disorders Fifth Edition (DSM-5).
	 Diagnosis of "Probable Alzheimer's Disease" according to the National Institute of Neurological and Communicative Disorders and Stroke–Alzheimer's Disease and Related Disorders Association (NINCDS-ADRDA).
3	Patients who are \geq 55 and \leq 90 years of age at the time of obtaining informed consent.
4	 Patients who can be followed in the same environment (as described below) from at least 3 weeks before baseline evaluation up to the completion of the examinations scheduled at the completion or discontinuation of investigational medicinal product (IMP) administration. Patients who will be hospitalized in the same medical facility.
	• Patients who will be institutionalized in the same care facility.
	• Patients who will continue to receive care at home. For patients receiving day care or day service, those patients who will visit the same care facility at the same frequency during the above-mentioned period will be included.
5	Patients whose caregiver can properly collect the necessary information (the main caregiver must observe the patient's condition in at least 4 days per week for 4 hours or more a day) Patients receiving home care must live with a specific caregiver and must not live alone.

Tab	ble 3.4.2-1 Inclusion Criteria
6	Patients with a Mini-Mental State Examination (MMSE) total score of ≥ 1 to ≤ 22 at screening.
7	
8	Patients who have agitation that interferes with daily activities and is persistent/recurs frequently during the 2 weeks each before the screening examination and baseline evaluation. Agitation is defined according to the "Consensus provisional definition of agitation in cognitive disorders" from
	the International Psychogeriatric Association (IPA). ^a
9	 Patients who have shown verbal aggression or physical aggression for 3 times or more during the 2 weeks before baseline evaluation. Examples of verbal aggression and physical aggression include the following symptoms in the "Consensus provisional definition of agitation in cognitive disorders" of IPA.^a Verbal aggression: yelling, speaking in an excessively loud voice, using profanity, screaming, shouting, etc.
	• Physical aggression: grabbing, shoving, pushing, resisting, hitting others, kicking objects or people, scratching, biting, throwing objects, self-hitting, slamming doors, tearing things, destroying property, etc.
10	Patients who show significant improvement (of two grades or more) in CGI-S from screening to baseline evaluation.
11	Patients who show inadequate response to nonpharmacological therapy for agitation associated with dementia of the Alzheimer's type or who are otherwise judged to be in need of pharmacological therapy.
12	Patients who are either capable of walking on their own or are able to move about with the use of a walking aid (a walker or wheelchair) and whose vision and hearing are sufficient to enable the required tests and observations for the trial (the use of glasses, hearing aids, etc, is acceptable).

^a Cummings J, Mintzer J, Brodaty H, Sano M, Banerjee S, Devanand DP, et al. Agitation in cognitive disorders: International Psychogeriatric Association provisional consensus clinical and research definition. International Psychogeriatrics. 2015;27:7-17.

[Rationale for inclusion criteria]

- This criterion is specified for ethical considerations. 1.
- 2. This criterion is specified because DSM-5 is recommended in the Practice Guideline for Dementia 2017, and NINCDS-ADRDA is widely used in clinical trials for dementia of the Alzheimer's type. These standards have been established as the diagnostic standards for dementia of the Alzheimer's type.
- 3. Although it is known that most patients with dementia of the Alzheimer's type are above the age of 65, there is a small number of patients below the age of 65. Past trials have suggested that patients of ages 55 and above may be suitable for such trials. Thus, the lower age limit was set at 55. On the other hand, given that patients aged over 90 could interfere with the evaluations set for this trial and in consideration of safety, 20 the upper age limit was set at 90.

- These patients were included because the target subjects of this trial, namely, patients with agitation 4. associated with dementia of the Alzheimer's type, may not necessarily be hospitalized patients but may be receiving care at nursing homes or at home. This criterion was also set for the appropriate assessment of the safety and efficacy of brexpiprazole.
- 5 to 12. These criteria are specified for the appropriate assessment of the safety and efficacy of brexpiprazole in the treatment of agitation associated with dementia of the Alzheimer's type.

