3.7 Measures to Minimize/Avoid Bias

Subjects who meet all the inclusion criteria and do not fall under any of the exclusion criteria will be randomly assigned to the brexpiprazole 1 mg/day group, the brexpiprazole 2 mg/day group, or placebo group at a randomization ratio of 3:4:4. The IMP allocation will be performed using a dynamic allocation method. The details of the randomization method will be described in a separately produced procedural guide for dynamic allocation.

This is a double-blind trial. The IMP allocation manager will prepare a "Table of randomization scheme and codes" (hereinafter randomization table) and conduct IMP coding according to the operating procedures for randomization. The IMP allocation manager will prepare an emergency code list for emergencies, such as when an SAE occurs.

The treatment assignment code will be revealed to neither the subject (including any representatives or caregivers) nor the investigator. The sponsor's staff involved in the

trial (except for those of the Department of Pharmacovigilance [PV department]), including contract research organizations (excluding the bioanalytical laboratory, genetic analysis laboratory, and IDMC), will also remain blind to the treatment assignment codes for the duration of the trial. Prior to the start of the trial, those who are involved in packaging the IMP and the sponsor will confirm that the IMP is not identifiable. The randomization table will be strictly retained until unblinding is performed after finalization of all the case report forms (CRFs) and database.

The emergency code break information will be managed by the IWRS until the completion of the trial. In the event that a subject has a medical emergency and the knowledge of the treatment assignment code is necessary for treatment, the emergency key may be opened for the subject in question (see Section 5.6 Procedure for Breaking the Blind).

The results of CYP2D6 genotyping and plasma drug concentration measurements should not be disclosed until unblinding at the end of the trial. The CYP2D6 genotyping and plasma drug concentration measurements should be performed at the designated laboratories and not at the clinical laboratories of the trial sites.

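### As worded in English, inclusion criterion 10 admits only patients whose CGI-S improved by two or more grades before baseline; it is probably reversed and must be checked

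*Protocol*

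**What the plan says.** Protocol Section 3.4.2 introduces the table with "Subjects must meet the inclusion criteria described in Table 3.4.2-1", and criterion 10 in that table is "Patients who show significant improvement (of two grades or more) in CGI-S from screening to baseline evaluation". Section 3.7 makes the table binding at allocation: "Subjects who meet all the inclusion criteria and do not fall under any of the exclusion criteria will be randomly assigned".

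The neighbouring criteria describe a different kind of patient:

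- Criterion 8: "Patients who have agitation that interferes with daily activities and is persistent/recurs frequently", over the two weeks before screening and again over the two weeks before baseline.
- Criterion 9: "Patients who have shown verbal aggression or physical aggression for 3 times or more during the 2 weeks before baseline evaluation".
- Criterion 11: "Patients who show inadequate response to nonpharmacological therapy for agitation associated with dementia", or a judgement on other grounds that drug therapy is needed.

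The only rationale for criterion 10 is the line shared by criteria 5 to 12: "These criteria are specified for the appropriate assessment of the safety and efficacy of brexpiprazole in the treatment of agitation". Section 3.2.2 describes the population this way: "Since this trial will be conducted in patients with aggression who have a strong need for medication among patients with agitation".

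**The concern.** Without a negation, criterion 10 makes marked improvement during screening a condition of entry. A trial of a drug for persistent agitation has no evident reason to require that, and the protocol gives none.

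Three things are at stake if the wording was followed:

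- **Population.** The sample would consist of patients who had already improved during screening. The effect size and SD in Section 6.1 come from an overseas trial and might not carry over.
- **Withdrawals and deviations.** Section 3.9.3.2 lists failure to meet the entry criteria among the grounds for mandatory withdrawal. SAP 7.6 counts eligibility deviations, and separately counts failures to discontinue subjects who met a withdrawal criterion. Under the published wording an enrolled non-improver could appear under both headings. Under a negated wording, the improvers could.
- **Interpretation.** A reader of the English protocol cannot tell who was eligible.

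**Working it through.** **1. Is the rule operative?** Yes. Table 3.8-1 schedules CGI-S at both screening and baseline, and Section 3.8.1.2 has eligibility confirmed again at baseline. A site can therefore compute the change and apply the criterion.

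**2. Does anything correct it?** Nothing in the available text does.

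| Place | What it has on CGI-S change before baseline |
|---|---|
| Synopsis, main criteria | Nothing (weak evidence, since only the main criteria are listed) |
| Table 3.4.3-1, exclusion criteria 1 to 31 | Nothing |
| Rationale in Section 3.4.2 | Generic line for criteria 5 to 12 |
| SAP | Nothing |

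Criterion 7 is blank in the public copy, and some closing protocol pages were not available, so those could not be checked.

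**3. Is it a strict contradiction?** No. A patient could improve by two grades and still have frequently recurring agitation, three aggressive episodes in two weeks and a need for medication. The criteria pull in different directions but can all be met at once. That the sentence is reversed is inferred from the target population and from the English text being a translation (the title page gives 24 Nov 2022 for Version 6.0 and 12 Jan 2023 for the translation).

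**4. Size of the eligibility effect.** Let p be the share of otherwise eligible patients who improve by two or more CGI-S grades. The documents do not give p; 2% to 30% is assumed. The target is 407 randomized (Section 3.3.1) at about 120 sites (synopsis).

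- Literal wording: share barred = 1 − p; otherwise eligible patients needed = 407 / p.
- Negated wording: share barred = p; needed = 407 / (1 − p).

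| p | Literal: barred | Literal: needed (per site) | Negated: barred | Negated: needed (per site) |
|---|---|---|---|---|
| 0.02 | 98% | 407/0.02 = 20,350 (169.6) | 2% | 407/0.98 = 416 (3.5) |
| 0.30 | 70% | 407/0.30 = 1,357 (11.3) | 30% | 407/0.70 = 582 (4.8) |

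**5. Power, as background.** Inputs from Section 6.1: difference 5.35 in absolute value, SD 15.06, two-sided 5%, 148 v 148 (2 mg) and 111 v 148 (1 mg). For a two-sample t-test the noncentrality is 5.35 / [15.06 × √(1/n₁ + 1/n₂)].

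- 2 mg: 5.35 / (15.06 × √(2/148)) = 3.06 on 294 df, power 86.1%.
- 1 mg: 5.35 / (15.06 × √(1/111 + 1/148)) = 2.83 on 257 df, power 80.5%.

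Both match the plan. If a selected sample moved the true difference by 10% or 20% either way at the same SD (an assumption, direction unknown), the results are:

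| True difference | 2 mg | 1 mg |
|---|---|---|
| 4.28 (−20%) | 68.3% | 61.6% |
| 4.815 (−10%) | 78.3% | 71.8% |
| 5.885 (+10%) | 91.8% | 87.3% |
| 6.42 (+20%) | 95.5% | 92.3% |

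This shows only how sensitive power is to the effect assumption. It is not an estimate of what criterion 10 did.

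**The case against.** The strongest reply is that this is a slip in the English copy and not a flaw in the trial. The sites are in Japan and probably worked from the original-language text. If that text carries the negation, conduct was sound and only an erratum is due. That is plausible and may well be right, but the documents do not show it.

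It is also fair that the enrollment and power scenarios assume a literal use that probably did not happen, with shares and shifts that have no source in the documents. They are illustrations, and the point does not rest on them.

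Two safeguards deserve mention. Section 3.8.1.1 has the medical monitor review eligibility before the baseline examination, but that review cannot settle a change that is known only once baseline CGI-S is rated. Section 3.14 provides for a joint decision by investigator and sponsor on whether a subject enrolled against the criteria continues. That softens the withdrawal consequence, but it removes neither the withdrawal ground in Section 3.9.3.2 nor the deviation count in SAP 7.6.

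Finally, the tension with criterion 11 is loose, since that criterion does not address CGI-S change. The weight lies on how implausible the wording is for this population, more than on any clash between two criteria.

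**Conclusion.** The point holds and must be fixed. Confidence in the literal reading is high: criterion 10 is an affirmative, binding entry condition, and no available text modifies it. That it is reversed is probable but inferred.

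The enrollment figures rest on the assumed 2% to 30% share, and the power figures on the assumed shifts in effect. Both matter only if sites applied the wording literally, which the documents do not show.

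The between-arm randomized comparison is not biased by this. Full analysis set membership (protocol 6.2.2, SAP 5.2) depends on randomization, at least one dose, and baseline and post-baseline CMAI data, so eligibility does not enter. What remains open is who the trial population is and how eligibility deviations are to be counted.

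**What to change.** Compare criterion 10 with the original-language protocol and with the sponsor's eligibility form described in Section 3.8.1.1, and reconcile it with criteria 8, 9 and 11. If the reversal is confirmed, add the missing negation or move the sentence to the exclusion table (Table 3.4.3-1). In either case, document how the criterion was applied to subjects already enrolled, so that the SAP 7.6 eligibility deviations are counted against the rule as confirmed.

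The cost is a one-line erratum or amendment, a check of two documents and a short note. No patients or procedures are added.
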